#### 6.1.7.3. NPRS-AUC3d

The calculation will include all assessments from baseline to Day 3. The procedures for dealing with missing data are described in [Section 6.1.4](#). See [section 6.1.7.14](#) for definitions of Day 1, Day 2, and Day 3.

In order to standardize the duration of time for each NPRS-AUC3d calculation, the “Day 3” NPRS will be set at exactly 48 hours regardless of when it was actually assessed for this endpoint, with two exceptions:

- 1) For patients whose “Day 3” score was assessed prior to Day 3 (prior to 36 hours) and whose score is higher at the “Day 7” assessment than at the “Day 3” assessment, we will linearly interpolate between the “Day 3” and “Day 7” scores to impute the score at 48 hours.
- 2) For patients whose “Day 3” occurs more than 12 hours after 48 hours (60 hours), we will linearly interpolate between “Day 2” and “Day 3” to impute the score at 48 hours.

The AUC will be calculated using the trapezoidal rule: average the NPRS scores between two adjacent timepoints, multiply by the difference in time points in hours, repeating this across all time points and summing the results to obtain the total AUC across a fixed range of time. Thus the AUC at a particular timepoint  $j$  is calculated as follows.

$$AUC_j = \frac{1}{2} (NPRS_j + NPRS_{j-1})(t_j - t_{j-1})$$

where  $t$  is measured in hours;  $j = 1, \dots, J$ ; and  $J$  is the total number of timepoints at which NPRS is measured.  $J = 5$  if all planned NPRS assessments are performed. Thus the total AUC for subject  $i$  from baseline to Day 3 is as follows.

$$AUC_{i, \text{BL to Day 3}} = \frac{1}{2} \sum_{j=1}^J (NPRS_{i,j} + NPRS_{i,j-1}) (t_{i,j} - t_{i,j-1})$$

Thus AUC is calculated for each subject with baseline and post-baseline NPRS scores, subject to the constraints on missingness described above.

#### **6.1.7.4. Complete SSS**

The complete SSS will be calculated from responses to all system sections of the SSS. The sum of the values of the 7 subsections will be the total SSS used to calculate the total complete SSS score.

#### **6.1.7.5. Coagulation Abnormalities**

Coagulation laboratory values (PT, PTT, platelets, and fibrinogen) will each be analyzed separately. For these analyses, each value at each time point will be categorized following the criteria established in the Snakebite Severity Score (Dart et al., 1996). Additional details are provided in [Section 8.2.3](#).

#### **6.1.7.6. Hemolysis**

The assessment of hemolysis will be based on free hemoglobin concentration (mg/dL), which will be treated as a continuous variable.

#### **6.1.7.7. Antivenom Administered**

The amount of antivenom administered will be categorized into three groups: low, medium, and high. The relevant value for these categorizations will be the total vials of antivenom given to the patient for which the treatment was initiated after the receipt of study drug. (Antivenom given to patients before the receipt of study drug will not be included in this total.) The categorizations are defined below, separately for each of the major types of antivenom:

##### India Polyvalent Antivenom (includes all antivenom given to participants in India)

Low: 0 vials  
Med: >0 to 10 vials  
High: >10 vials

##### CroFab

Low: 0 vials  
Med: >0 to 6 vials  
High: >6 vials

##### ANAVIP

Low: 0 vials  
Med: >0 to 10 vials

High: >10 vials

#### **6.1.7.8. Time from Initiation of Ventilatory Support to Initiation of Weaning**

The total time from initiation of ventilatory support to initiation of weaning will be calculated in hours. Subsequent re-intubations will not be included in this calculation.

#### **6.1.7.9. Duration of Ventilatory Support**

The duration (hours) of ventilatory support for primary neurotoxic envenoming will be calculated as the total duration of mechanical (ventilator) or manual (bag valve mask) methods used to assist or replace spontaneous respiration. If a subject is reintubated one or more times, these additional periods of ventilatory support (from initiation of ventilatory support to extubation or removal of ventilatory support) will be included as part of the total time.

$$\sum_{\text{for each ventilation}} (\text{time of removal of support} - \text{time of initiation of support})$$

#### **6.1.7.10. Duration of ICU Stay**

The length of ICU stay from baseline to Day 28 will be calculated using the following duration in hours

$$\sum_{\text{for each episode}} (\text{ICU discharge date and time} - \text{ICU admission date and time})$$

The duration of ICU stay will be truncated at Day 28. If a discharge date and time is after Day 28, it will be replaced by Day 28.

#### **6.1.7.11. Duration of hospitalization**

The length of hospital stay from baseline to Day 28 will be calculated using the following duration in hours

$$\sum_{\text{for each admission}} (\text{discharge date and time} - \text{admission date and time})$$

The duration of hospitalization will be truncated at Day 28. If a discharge date and time is after Day 28, it will be replaced by Day 28.

#### **6.1.7.12. Treatment-Emergent Adverse Event**

Treatment-emergent AEs are defined as AEs that first occur or worsen in severity after the first dose of IP and prior to 30 days after last administration of IP.

Where an AE start date/time or end date/time is partially or fully missing, and it is unclear as to

whether the AE is a TEAE, it will be assumed that it is TEAE.

#### **6.1.7.13. Percent of Study Medication Compliance**

The percent of study medication compliance will be calculated as follows:

$$100 * \sum_{i=2}^{\text{last visit}} \frac{\text{Number of oral doses dispensed at visit } (i-1) - \text{Number of oral doses returned at visit } i}{\text{Number of oral doses that the subject was instructed to take from visit } (i-1) \text{ to visit } i}$$

where the denominator is greater than zero.

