- s PLA₂ sampling will be performed for all subjects on Day 1 (pre-dose and 1, 3, 6, and 9 hours post-first dose), and on Day 2, Day 3, and Day 7 (pre-dose). sPLA₂ in serum and PK samples will be processed and analyzed in a central laboratory, not at individual sites.
- PK sampling will only be performed for a total of 20 adult and pediatric subjects on Days 1 and 3, and all subjects on Day 7. Once 20 subjects have provided PK samples for Days 1 and 3, sites will be notified by the sponsor to discontinue Day 1 and 3 PK sampling. Subjects will be enrolled for PK analysis as follows: Day 1 20 subjects, pre-dose and 0.5, 1, 2, 4, 6, 8, and 12 (pre-second dose) hours; Day 3 20 subjects, pre-dose and 0.5, 1, 2, 4, 6 hours; Day 7 all subjects, pre-dose.

Figure 1 Study Schematic

- a. Because snakebite subjects are considered critically ill and will arrive in an emergency department setting, Screening, Baseline evaluation, randomization, and treatment must all take place on Study Day 1
- b. Assessments (see Schedule of Events) must be performed at the following times post-initial dose: 3 to 4 hours, 5 to 6 hours, 8 to 10 hours, 2 days (12 to 18 hours after last Day 1 measurements), 3 days (approximately 24 hours after Day 2 measurements), 7 days ± 1 day, 14 days ± 2 days, and 28 days ± 3 days
- c. The varespladib-methyl dosing for adult subjects is a 500 mg loading dose, a 250 mg dose approximately 12 hours later, then 250 mg BID for the remainder of the study period; pediatric subjects (ages 5 to < 18) will be administered doses of varespladib-methyl determined by allometric scaling, provided as 50 mg capsules, depending on age (see Section 7.3). Abbreviations: BID = twice daily; SOC = standard of care; yr = years

3		TABLE OF CONTENTS	
1	APF	PROVAL SIGNATURES	2
2	PRO	OTOCOL SUMMARY	3
	2.1	Synopsis 3	
	2.2	Schedule of Events	9
3	TAI	BLE OF CONTENTS	14
	3.1	List of In-text Tables	18
	3.2	List of In-text Figures.	18
4	LIS	Γ OF ABBREVIATIONS AND DEFINITION OF TERMS	19
5	INT	RODUCTION	20
	5.1	Background and Rationale	

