7.3 Selection of Doses in the Study

LY333013 (varespladib-methyl) is formulated in an immediate-release film-coated oval tablet at a unit dosage strength of 250 mg for oral administration. Ophirex is developing varespladib-methyl (LY333013) for oral administration for 7 days total for the treatment of venomous snakebites. LY333013 is a prodrug that is rapidly metabolized to LY315920; LY315920 is a potent inhibitor of sPLA₂ in vitro and in vivo.

This study evaluates the safety, tolerability, and efficacy of varespladib-methyl in subjects bitten by venomous snakes from diverse regions and snake genera, including (but not limited to) pit vipers (e.g., rattlesnake, copperhead), vipers (e.g., Russell's viper and saw-scaled viper), and elapids (e.g., coral snake, cobra, krait).

The proposed dosing of varespladib-methyl for adult subjects consists of an initial loading dose of 500 mg ($2 \times 250 \text{ mg}$ oral tablet) varespladib-methyl upon randomization, followed by dosing with 250 mg varespladib-methyl ($1 \times 250 \text{ mg}$ oral tablet) approximately 12 hours later, followed by BID dosing with $1 \times 250 \text{ mg}$ varespladib-methyl oral tablets for the remainder of the 7-day treatment period.

Pediatric subjects (ages 5 to < 18) will be administered doses of varespladib-methyl determined by allometric scaling, provided as 50 mg capsules, depending on age. Pediatric doses were determined based on the 250 mg BID adult dose. Median weights from the Centers for Disease Control (CDC) growth charts were used for the allometric scaling, with weights averaged for male and female pediatric subjects. Subjects 5 to < 11 years old will receive an initial loading dose of 200 mg varespladib-methyl, an additional dose of 100 mg approximately 12 hours later, followed by 100 mg BID. Subjects 11 to < 18 years old will receive a loading dose of 400 mg varespladib-methyl, an additional dose of 200 mg approximately 12 hours later, followed by 200 mg BID. Including the loading dose, subjects will receive a total of 14 doses of study medication. Dosing may occur on 7 or 8 calendar days, depending on whether the first dose of study medication is in the morning or the afternoon.

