10.2 Study Periods and Visits

10.2.1 sPLA₂ and Pharmacokinetics Sample Timing

Note that the sPLA₂ and PK sample collection will be performed with a different timing than the other assessments, as described in the Schedule of Events (Table 1).

Specifically, PK sampling will only be performed for a subset of adult and pediatric subjects on Days 1 and 3 and all subjects on Day 7 as described in Section 10.3.2.1. Subjects will be enrolled for PK analysis as follows: Day 1 - 20 subjects, pre-dose and 0.5, 1, 2, 4, 6, 8, and 12 (pre-second dose) hours; Day 3 - 20 subjects, pre-dose and 0.5, 1, 2, 4, 6 hours; Day 7 - all subjects, pre-dose. Special attention should be paid to collection of PK samples on Day 1 of this protocol.

sPLA₂ sampling will be performed for all subjects on Day 1 (pre-dose and 1, 3, 6, and 9 hours post-first dose), and on Day 2, Day 3, and Day 7 (pre-dose).

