10.2.3.9 Day 7 (7 Days \pm 1 Day)

- Continue BID oral treatment with the IP
- Perform physical examination
- Measure vital signs per institutional practice
- Perform individual assessments pertaining the SSS (clinical evaluation of the actual SSS point score will be performed after completion of the study):
 - Local wound severity
 - Pulmonary severity
 - Cardiovascular severity
 - Gastrointestinal severity
 - Hematologic severity
 - Renal severity
 - Nervous system severity
- Measure Head-Lift duration (0 to 5 seconds)
- Perform NPRS
- 12-lead ECG
- Measure grip strength
- Collect blood and urine for the following laboratory assessments:
 - CBC
 - Serum chemistry
 - LFTs
 - PT, PTT, thrombin time, INR
 - Absolute fibrinogen
 - Urinalysis
 - sPLA₂ levels as described in Section 10.2.1
 - Biomarkers (CRP, and D-dimer)
- Collect PK samples from all subjects as described in Section 10.3.2.1
- Perform CGI-I

OPX-PR-01

- Perform PGIC
- Perform PSFS
- Assess C-SSRS (Since Last Visit Form)
- In sedated, endotracheally intubated subjects, perform additional assessments according to instructions in Section 10.3.1.7
- Record concomitant medications and therapies (e.g., prescription and nonprescription medications, pain medications)
- Continue SOC treatment
- Record hospitalization details
- Record pulmonary support interventions
- Assess and Record AEs

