### 7.4. Exposure and Compliance

IP exposure and dosing information including the number of doses per subjects and amount of IP received will be tabulated by treatment arm and age group.

For each treatment, IP compliance will be summarized by compliance category ( $\leq 80\%$ , 80-120%,  $\geq 120\%$ ) and the number of subjects in each compliance category. Study medication compliance will also be summarized as a continuous variable using descriptive statistics. This

analysis will be conducted for the SAF population.

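### SAP 6.1.7.13 adds up visit-level compliance ratios instead of dividing totals, so a fully compliant patient scores 100% times the number of dosing intervals

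*SAP*

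**What the plan says.** SAP 6.1.7.13 (Percent of Study Medication Compliance) gives an equation: 100, times a sum from visit 2 to the last visit, of a fraction. The numerator is doses dispensed at the previous visit minus doses returned at the current one. The denominator is the "Number of oral doses that the subject was instructed to take from visit" to visit. A single summation sign stands in front of the whole fraction, and the condition attached is "where the denominator is greater than zero".

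SAP 7.4 (Exposure and Compliance) then says "IP compliance will be summarized by compliance category", with limits of ≤80%, 80-120% and ≥120%. It also summarises the percentage as a continuous variable, in the Safety population.

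On dosing, Protocol 7.3 says "Including the loading dose, subjects will receive a total of 14 doses of study medication" and "Dosing may occur on 7 or 8 calendar days". The schematic notes in Protocol 2.2 place visits during this period on Day 1, Day 2, then "3 days (approximately 24 hours after Day 2 measurements), 7 days ± 1 day". The Day 7 PK sample is described as "Day 7 - all subjects, pre-dose" (Protocol 10.2), and the Day 7 visit includes the instruction "Continue BID oral treatment with the IP" (Protocol 10.2.3.9). Neither document says at which visits study drug is dispensed and returned for the purpose of this formula.

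**The concern.** A compliance percentage should compare all doses taken with all doses due. A sum of ratios does not: each interval contributes up to 100% by itself, and a short interval counts as much as a long one. A patient who took everything is then reported far above 100% and placed in the category that looks like overuse. A patient who stopped early can be placed in the middle category, which looks like good adherence. Dosing after discharge is recorded by the patient (Protocol 9.4), so adherence outside hospital is something a reader of the study report will want to see stated correctly.

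**Working it through.** **Inputs.** Total doses: 14 (Protocol 7.3). Visits: Days 1, 2, 3, 7, 14 and 28 (Protocol 2.2). Formula: SAP 6.1.7.13. Categories: SAP 7.4. Two assumptions are mine: doses every 12 h from 0 to 156 h, and visits at 0, 24 and 48 h with Day 7 at 120, 144 or 168 h. The number of intervals, k, is not stated in the documents, so it is varied.

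**The plan's own figure.** 1 loading dose + 13 further doses = 14, and 7 days × 2 per day = 14. The stated total is reproduced. The documents give no worked compliance percentage to reproduce.

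**Full adherence.** Each interval with instructed doses contributes 1, so the printed score is 100 × k:

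| Case | Instructed doses per interval | Printed score | Ratio of totals |
|---|---|---|---|
| One interval only | 14 | 100% | 14/14 = 100% |
| Day 7 visit at 168 h, after the last dose | 2, 2, 10 | 300% | 14/14 = 100% |
| Day 7 visit at 144 h, pre-dose | 2, 2, 8, 2 | 400% | 14/14 = 100% |
| Day 7 visit at 120 h | 2, 2, 6, 4 | 400% | 14/14 = 100% |

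Intervals after the last dose have a zero denominator and drop out.

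**Early stopping.** The patient takes both doses before Day 2 and none later. Printed: 2/2 + 0/2 + 0/10 = 1, or 100%. With the four-interval split, 2/2 + 0/2 + 0/8 + 0/2 is also 100%. Ratio of totals: 2/14 = 14%. Dividing the printed sum by k would not repair it: 100/3 = 33% with three intervals, because a 2-dose interval would weigh as much as a 10-dose one.

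**Equal adherence in every interval.** A printed score of 80-120% corresponds to true intake of 80/3 to 120/3, about 27-40%, with three intervals, and 80/4 to 120/4, or 20-30%, with four.

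**Direction of the error.** With two or more dosing intervals, every interval denominator is smaller than the total of 14. So if no interval has negative net doses, the printed score exceeds the true one for any patient who took at least one dose.

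**Single dispensing does not necessarily rescue the formula.** If all 14 doses are logged as dispensed on Day 1, nothing is returned at Day 2 and every visit is used, the Day 2 term alone is 14/2 = 700%.

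**The case against.** The strongest reply has three parts.

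1. **The number of intervals is not stated.** If drug is dispensed once and returned once, k = 1 and the formula gives the right answer. This stands as a limit on the size. A reader might infer that the plan itself implies one fixed wrong value, such as 200% or 300%. It does not: the text supports only 100% times k, and the 300-400% figure needs the protocol visits as the intervals. That assumption is reasonable, since the sum is indexed by visit up to the last one and SAP 6.1.5 ties analyses to the protocol schedule, but it remains an assumption.

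2. **The equation was read from PDF by a program.** The original might place separate sums in numerator and denominator. The condition on the denominator favours the printed form: a total over the whole treatment period would hardly need it, whereas intervals after the last dose do. That is support, not proof.

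3. **The consequences are small.** A reader might infer that under-dosing would go unseen, or that the per-protocol set or an efficacy result would be affected. The documents do not support this. SAP 7.4 separately tabulates the number of doses and amount of study drug received, and Listing 16.2.5.1 shows exposure by subject. The per-protocol population is defined by significant protocol deviations (SAP 5), not by this percentage, and the primary and key secondary models do not use it. Protocol 13.1.3 asks only for a listing of doses and amount. Routine values of 300% or more would also be noticed once the table was run.

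All of this limits the impact. None of it corrects the formula, and no other section does so.

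**Conclusion.** The formula is wrong as printed. A fully compliant patient scores 100% times the number of intervals with instructed doses. On the protocol visit schedule that is 300%, or 400% when doses remain after the Day 7 visit, and the patient falls in the ≥120% category. The middle category can hold a patient with 14% true intake. The size rests on taking the protocol visits as the dispensing and return intervals; with one interval there is no error. The finding also depends on the summation sign standing where the extracted text shows it. The damage is limited to descriptive output in the Safety population: the compliance categories and the continuous summary in Table 14.1.6, and Listing 16.2.5.1. It is worth correcting because the percentage would be misleading and the correction is simple.

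**What to change.** Replace the equation in SAP 6.1.7.13 with:

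compliance = 100 × Σ(dispensed − returned) / Σ(instructed),

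both sums taken over all intervals with instructed doses. This returns 14/14 = 100% for the fully compliant patient in every scenario above and 2/14 = 14% for the early stopper. Check the summation sign against the original PDF before amending.

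As a minor tidy-up, make the SAP 7.4 categories non-overlapping: <80%, 80-120%, >120%. With 14 instructed doses the boundaries cannot be hit exactly (80% is 11.2 doses, 120% is 16.8), so the overlap matters only for patients with another instructed total, such as 5 or 10.

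The cost is one formula and one line of category limits. No new data and no change to trial conduct are needed.

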#### **6.1.7.14. SSS Score using Compressed SSS Scale**

The compressed SSS will be calculated by first subtracting 1 from non-zero responses to the pulmonary, cardiovascular, hematologic, renal, and nervous system sections of the SSS. The sum of the adjusted values of the 5 subsections will be the total SSS used to calculate the compressed score. The endpoint will be the change from baseline through Day 7 compressed scores: Change = Baseline – Score (at each time).

#### **6.1.7.15. Data Adjustments/Handling/Conventions**

All collected data will be presented in listings. Data not subject to analysis according to this plan will not appear in any tables or graphs but will be included only in the data listings.

Day 1 will refer to activities that occurred at baseline through the first 12 hours after the patient receives the study drug (regardless of whether the calendar day has changed). Day 2 assessments will occur at least 12 hours and not more than 18 hours after the 8-10 hour assessment on Day 1. Thereafter, Day will refer to calendar day following the initiation of treatment (e.g., Day 28 will occur 27 days after the day on which the patient received their first dose of study drug).

*P* values will be displayed with two significant figures if the value is greater than or equal to 0.01 (eg., 0.XX) and with one significant figure is less than 0.01 (eg., 0.00X). If a *P* value less than 0.0001 occurs, it will be shown in tables as < 0.0001.

Adverse events will be coded using the latest MedDRA version thesaurus.

### **6.1.8. COVID-19**

The potential impact of COVID-19 on this clinical trial and trial participants will be described in listings and in the CSR.

The following aspects will be summarized when protocol deviations are due to COVID-19 infection or restriction:

- Changes to treatment dispensation
- Changes to treatment administration
- Changes to visit windows to accommodate delays for some assessments

- Missing efficacy endpoints
- Missing visits

## 7. Study Subjects and Demographics

### 7.1. Disposition of Subjects and Withdrawals

Disposition will include tabulations by treatment group and overall:

- the number of subjects randomized into each treatment group
- the number of subjects who received treatment
- the number of subjects who received the entire course of treatment
- the number of subjects completing the study
- tabulated reasons for discontinuation from the study
- and number of subjects in each analysis population.

The total number of (1) screening failures and (2) withdrawals prior to receipt of study drug and the reasons for screen failure and withdrawals prior to receipt of study drug will be presented in separate tables.

### 7.2. Protocol Violations and Deviations

A by-subject listing of protocol deviations will be presented. Protocol deviations will also be reported by major vs. minor status. Protocol deviations classified as important will be re-classified as major; protocol deviations classified as non-important will be re-classified as minor.

### 7.3. Demographics and Other Baseline Characteristics

These analyses will be conducted for the ITT and SAF populations.

Summary statistics for age, gender, race, ethnicity, height, and weight will be presented by treatment group.

The envenoming history, including the anatomic location of envenoming, initial swelling, snake identification, key toxicities as measured in Baseline SSS subscores, and tourniquet use will be summarized by treatment group. If obtained, results of the 20WBCT will also be summarized by treatment group.

The number and percent of subjects reporting various medical histories, grouped by MedDRA system organ class and preferred term, will be tabulated by treatment group.

